### **Additional Subgroup Analysis Populations**

Subgroup analyses of the primary endpoint will be performed on subgroups as defined below if needed. For the definition of subgroup, data as documented in the electronic case report form (eCRF) will be taken.

#### **Subgroups:**

The following subgroups will be defined if the data suggest a possible imbalance between the two arms:

- the number of embryos transferred
  - 1 embryo transferred
  - 2 embryos transferred

## **9 General Specifications for Data Analyses**

### **Study intervention groups**

Study intervention groups are defined and labelled as Crinone® and combination medication (Crinone® plus Duphaston®).

Unless otherwise indicated all analyses will be presented separately for the two study intervention groups.

### **Data handling after cut-off date**

Data after cut-off do not undergo the cleaning process.

Data obtained after the cut-off will not be displayed in any listings or used for summary statistics, e.g. laboratory values of samples taken after data cut-off, AEs with onset date after data cutoff, etc. will not be included in any analysis or listing.

Stop dates are not affected by this rule, e.g. a stop date of AEs, which starts prior to the cut-off, but stops after date of cut-off, will not be changed.

## **Significance level**

There is no formal statistical hypothesis testing in this study. For treatment difference, two sided 90% confidence intervals will be calculated, unless otherwise in this IAP specified.

## **Presentation of continuous and qualitative variables**

Continuous variables will be summarized using descriptive statistics, i.e.

- number of subjects, number of subjects with non-missing values,
- mean, standard deviation,
- median, 25th Percentile - 75th Percentile (Q1-Q3),
- minimum, and maximum.

Qualitative variables will be summarized by counts and percentages.

Unless otherwise stated the calculation of proportions will be based on the number of subjects of the analysis population of interest. Therefore, counts of missing observations will be included in the denominator and presented as a separate category.

In case the analysis refers only to certain visits percentages will be based on the number of subjects still present in the study at that visit, unless otherwise specified.

## **Definition of baseline**

In general, the last non-missing measurement prior to ( $\leq$ ) randomization date will serve as the baseline measurement. If no such a value is available, the last measurement prior to ( $\leq$ ) the first study intervention administration date after randomization date will be used as the baseline measurement.

## **Conversion factors**

The following conversion factors will be used to convert days into months or years: 1 month = 30.4375 days, 1 year = 365.25 days.

## **Handling of missing data**

Unless otherwise specified, missing data will not be replaced.

In all subject data listings, imputed values will be presented. In all listings imputed information will be flagged.

Missing statistics, e.g. when they cannot be calculated, should be presented as “nd”. For example, if n=1, the measure of variability (SD) cannot be computed and should be presented as “nd”.

## **Time window**

Day 1 is the day of start of study intervention after randomization, the day before is Day -1 (no Day 0 is defined).

Study day is defined relative to Day 1.

#### **Software(s)**

All analyses will be performed using SAS® Software version 9.4 or higher.

## **10 Study Subjects**

The subsections in this section include specifications for reporting subject disposition and study intervention/study discontinuations. Additionally, procedures for reporting protocol deviations are provided.

### **10.1 Disposition of Subjects and Discontinuations**

- Total number of subjects screened (i.e. subjects who gave informed consent)
- Number of subjects who discontinued from the study prior to randomization overall and grouped by the main reason (e.g. the failed specific inclusion or exclusion criteria, withdraw of consent)
- Number of randomized subjects.
- Number of randomized subjects who received at least one dose of study intervention after randomization
- Number of randomized subjects who completed study after randomization, grouped by study intervention group and main reason.
- Number of randomized subjects who discontinued the study after randomization, grouped by study intervention group and main reason

The number and percentage of subjects in each of the above disposition categories will be presented by randomized study intervention group (if applicable) and overall. Percentages will be presented with respect to the number of randomized subjects. Study completion or discontinuation and their corresponding reasons will be summarized from “Study Termination” eCRF page.

Disposition of subjects by allocated study intervention group will be presented in a CONSORT Flow Diagram.

The results of the randomization algorithm (according to IVRS) will be summarized as follows:

- Number of subjects by randomization stratum (IVRS)

## **10.2 Protocol Deviations**

### **10.2.1 Important Protocol Deviations**

The following summary tables and listings of important protocol deviations will be provided (separately for pre-/post inclusion deviations):

- Frequency table per reason of important protocol deviations
- Listing of important protocol deviations

### **10.2.2 Reasons Leading to the Exclusion from an Analysis Population**

For subjects excluded from the PP, the reasons for exclusion will be summarized and listed;

- Frequency table per reason of exclusion from the PP population
- Listing of reasons of exclusion from the PP population

## **11 Demographics and Other Baseline Characteristics**

If not stated otherwise, summaries will be presented on the ITT analysis population, by randomized study intervention group and overall.

### **11.1 Demographics**

Demographic characteristics will be summarized using the following information from the “Visit 1 (Baseline Evaluation)” eCRF pages.

- Demographic characteristics
  - Age at freezing (years)
  - Age at transfer (years)
  - Age categories at transfer:
    - < 35 years and  $\geq$  20 years
    - $\geq$  35 years
  - Race: Asian, other, not collected at this site
- Weight at Baseline
- BMI at Baseline

Specifications for computation in EDC:

- Age at transfer (years)
  - Formula: (date of given informed consent - date of birth) / 365.25.
  - In case of missing day for at least one date, but month and year available for both dates:  
For the derivation of age, the day of informed consent and the day of birth will be set to 1 and the formula above will be used
  - In case of missing month for at least one date, but year available for both dates:  
For the derivation of age, the day and the month of informed consent and the day and month of birth will be set to 1 and the formula above will be used
- BMI (kg/m^2) = weight (kg) / [height (cm) x height (cm)] x 10000

Deviation:

- Age at freezing (years)
  - Formula: (date of frozen embryo- date of birth) / 365.25.
  - Data Source: date of frozen embryo is from “Embryo Transfer” eCRF page.
  - Missing date imputation: same as the way as the one for age at transfer.

## 11.2 Medical History

The medical history will be summarized from the “Medical History” eCRF page, using MedDRA, current version, preferred term as event category and system organ class (SOC) body term as Body System category.

Medical history will be displayed in terms of frequency tables: ordered by primary SOC and PT in alphabetical order.

## 11.3 Other Baseline Characteristics

Information on disease characteristics and ET preparation collected at the baseline evaluation visit will be summarized by study intervention group and overall. Summary statistics will be presented for:

### **Disease history**

- Subjects with pelvic surgery history (“Pelvic Surgery History” eCRF page)
- Previous pregnancies (‘Yes’ or ‘No’) (“OBSTETRICAL HISTORY” eCRF page)
  - Definition: subjects with number of previous pregnancies >0 will be categorized to be ‘Yes’, otherwise ‘No’

- If Yes, number of previous pregnancies will be provided and displayed by number category.
- Live births ('Yes' or 'No') ("OBSTETRICAL HISTORY" eCRF page)
  - Definition: subjects with number of live births >0 will be categorized to be 'Yes', otherwise 'No'
  - If Y, number of live births will be provided and displayed by number category.
- Spontaneous abortions ("OBSTETRICAL HISTORY" eCRF page)
  - Definition: subjects with number of spontaneous abortions>0 will be categorized to be 'Y', otherwise 'N'
  - If Y, number of spontaneous abortions will be provided and displayed by number category.
- Therapeutic/elective abortions ("OBSTETRICAL HISTORY" eCRF page)
  - Definition: subjects with number of therapeutic/elective abortions>0 will be categorized to be 'Y', otherwise 'N'
  - If Y, number of therapeutic/elective abortions will be provided and displayed by number category.
- Infertility (primary or secondary) ("Infertility History" eCRF page)
- Duration of Infertility (Months) ("Infertility History" eCRF page)
- Type of Infertility ("Infertility History" eCRF)
  - Causes of female infertility

#### **Embryo transfer related baseline characteristics**

- Endometrial thickness at baseline ("Ultrasound Scan Assessment -Screening" eCRF page at visit 1)
- Duration of Estradiol Valerate prior to randomization date (day)
  - Derivation: randomization date - the date of Estradiol Valerate initiation + 1
  - Data source:
    - The date of Estradiol Valerate initiation: the first dose date in "Administration of Estradiol Valerate" eCRF page
    - Randomization date: randomization date in the "Randomization" eCRF page at visit 4
- Endometrial thickness prior to initiation of Crinone ("Ultrasound Scan Assessment-1" eCRF page at visit 3)
- Endometrial thickness at transfer day ("Ultrasound Scan Assessment-2" eCRF page at visit 4)
- Number of D5 embryos transferred (displayed by number category) ("Embryo Transfer" eCRF page)

- Duration of embryo frozen (months)
  - Formula: =embryo transfer date – the date of frozen embryo + 1
  - Data source: “Embryo Transfer” eCRF page
- Good quality embryo
  - Derivation: for each subject, it is the number of embryos graded in AA, AB, BA or BB (inner cell mass is not equal to 'C' and trophectoderm is not equal to 'C') according to the Gardner Embryo Grading System.
  - Data source: “Embryo Transfer” eCRF page

## 12 Concomitant Medications/Procedures

**Concomitant treatments** are medications, other than study interventions and estradiol valerate, which are taken by subjects any time on-study (on or after the first day of study intervention after randomization for each subject) or prior to last dose of trial drug.

Concomitant treatment will be summarized from the “Concomitant Medication” eCRF page. ATC-2nd level and preferred term will be tabulated as given from the WHO-DD dictionary current version. In case multiple ATC's are assigned to a drug, all ATC-2nd level will be used for reporting. In case the date values will not allow to unequivocally allocate a medication to concomitant medication, the medication will be considered as concomitant medication.

All **Concomitant procedures**, which were undertaken any time on study, will be summarized according to the eCRF page “Concomitant Procedures”. Concomitant procedures will be classified by medical review.

Number of subjects with concomitant procedures (on or after the first day of study intervention after randomization or prior to last dose of study intervention) will be presented by overall and by type of procedure (as classified by medical review)

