6.5.4 Other Interventions

Estradiol valerate will be administered according to local practice.

All participants will receive oral estradiol valerate continuously and the dose of estradiol valerate will be adjusted according to local practices.

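### SAP 12's *or* places no limit on what counts as concomitant, so drugs stopped before randomisation are pooled with later ones; separately, no planned output covers estradiol valerate after randomisation

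*SAP*

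**What the plan says.** **Definition.** SAP 12 states that concomitant treatments "are medications, other than study interventions and estradiol valerate, which are taken by subjects any time on-study". A parenthesis explains on-study as on or after the first day of study intervention after randomisation, and the sentence then adds "or prior to last dose of trial drug". Concomitant procedures get the same construction: "on or after the first day of study intervention after randomization or prior to last dose of study intervention". For unclear dates the section provides: "In case the date values will not allow to unequivocally allocate a medication to concomitant medication, the medication will be considered as concomitant medication".

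**Recording period.** Protocol 6.5 requires all concomitant therapies, including changes, to be recorded from informed consent until completion. Randomisation comes later, on the day of embryo transfer (Protocol 1.2 and 6.3.1). The SAP plans no separate table of prior medication.

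**Display.** SAP 9, on study intervention groups: "Unless otherwise indicated all analyses will be presented separately for the two study intervention groups".

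**Estradiol valerate.** Protocol 6.5.4, which sits under Concomitant Therapy, states: "All participants will receive oral estradiol valerate continuously and the dose of estradiol valerate will be adjusted according to local practices". SAP 12 takes the drug out of the concomitant table. SAP 13 bases all dosing summaries on the Crinone and Duphaston eCRF pages. The one estradiol summary in the SAP is in 11.3: "Duration of Estradiol Valerate prior to randomization date (day)".

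**The concern.** A concomitant-medication table in a randomised trial should show what was given alongside the allocated treatment once the arms had separated. Use that ended before randomisation is a baseline characteristic, expected to be similar in the two arms. Counting it in the same rows adds a common amount to each arm and makes a real post-randomisation difference harder to see. This matters here because the trial is open label, and because Protocol 6.5.1 and 6.5.3 let women who receive rescue medicine stay in the study, and also women who receive a prohibited progesterone if sponsor and investigator agree.

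The estradiol gap is a separate matter. All participants keep taking it after randomisation, with doses adjusted by local practice, and treating physicians know the allocation. If it were changed or stopped more often in one arm, a reader of the pregnancy and bleeding comparisons would want to know. No planned output would show it.

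**Working it through.** **1. What the *or* admits.** Let a drug run from start *s* to stop *e*. Day 1 is the first dose after randomisation (SAP 9, Time window) and *L* is the last dose.

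- As written, the drug counts if *e* ≥ Day 1 **or** *s* ≤ *L*.
- To fail, it would have to stop before Day 1 and also start after *L*. Since *L* cannot precede Day 1, this is impossible, so nothing is excluded.
- With **and**, the drug counts only if its use overlaps Day 1 to *L*.

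A count confirms the logic. Take 31 days before Day 1 and 89 days from Day 1 onward (120 days), with *L* assumed at Day 63.

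- Possible start/stop pairs: 120 × 121 / 2 = 7260. Under *or*, all 7260 qualify.
- Under *and*, pairs wholly before Day 1 drop out (31 × 32 / 2 = 496), as do pairs wholly after Day 63 (26 × 27 / 2 = 351). That leaves 7260 − 847 = 6413.

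These are possible date pairs, not patients. A drug taken only from Day −20 to Day −2, for example, qualifies under *or* and not under *and*.

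**2. The section's own intent.** The parenthesis ties on-study to the period after randomisation. The unclear-date rule has a purpose only if some drugs are not concomitant. SAP 15.1 defines the treatment period with two bounds, from the first dose after randomisation to the last dose or the clinical cut-off. The literal window fits none of these.

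**3. How much a contrast could be diluted.** The documents give no usage figures, so all inputs are assumed: 10% against 2% of the arms receive a given drug after randomisation (about 17 and 3 women, if the planned 334 split into 167 per arm), and a proportion *p* in both arms used it before randomisation, independently of later use. The table would show 1 − (1 − *p*)(1 − 0.10) against 1 − (1 − *p*)(1 − 0.02). The difference becomes (1 − *p*) × 8 percentage points.

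| Prior use *p* | Shown in table | Ratio | Difference (points) |
|---|---|---|---|
| 0% | 10.0% vs 2.0% | 5.0 | 8.0 |
| 2% | 11.8% vs 4.0% | 3.0 | 7.8 |
| 5% | 14.5% vs 6.9% | 2.1 | 7.6 |
| 10% | 19.0% vs 11.8% | 1.6 | 7.2 |
| 20% | 28.0% vs 21.6% | 1.3 | 6.4 |
| 40% | 46.0% vs 41.2% | 1.1 | 4.8 |

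**4. How much estradiol exposure goes unsummarised.** Appendix 4 allows at most 20 days before endometrial transformation, then 4 to 6 days to transfer: at most 24 to 26 days before randomisation. Assume the maximum before randomisation and use continuing to the visit concerned. The post-randomisation share is then:

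- to Day 14: 14/40 to 14/38, or 35% to 37%;
- to Day 63: 63/89 to 63/87, or 71% to 72%.

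Fewer days before randomisation would raise these shares.

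**5. Whether the data exist.** SAP 11.3 names an eCRF page for estradiol administration but cites it only for the first dose date. Appendix 4 lists estradiol data at Visits 1 to 3; Visits 4 to 6 list only concomitant medications. Protocol 6.5 nonetheless requires changes in concomitant therapy to be recorded to completion.

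**The case against.** The best reply on the window is that *or* is a slip for *and*, as step 2 suggests, and that a sensible programmer would read it so. That is probably right about intent. It does not rescue the text, which states the opposite twice and would give the wrong table if followed.

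A reader might infer that SAP 12 cannot show post-randomisation co-treatment by arm at all. The documents do not support that. By-arm display is the default in SAP 9, and a non-study progestogen added after randomisation will appear in its arm's column, mixed with earlier use. There is also a second route: SAP 8.1 counts post-inclusion deviations as important and SAP 10.2.1 tabulates them separately, so prohibited progesterone may surface there. That route does not cover rescue medicine, which Protocol 6.5.3 says is not prohibited.

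A reader might also take the 40% row above as the likely case and conclude that the table is swamped. Protocol 6.5.3 prohibits other progesterone in the month before and during the study, pre-randomisation Crinone is excluded as a study intervention, and use that ended before consent need not be recorded. For progestogens the lower rows are more plausible, and there the absolute difference barely moves.

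On estradiol, it is fair to say that local practice at a single centre is one practice shared by both arms, that nothing in the documents indicates differential adjustment, and that the trial is an exploratory pilot. All of that stands. The protocol does not say that physicians may change the dose freely; it refers to local practice without stating a rule.

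**Conclusion.** Two modest points hold.

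First, the SAP 12 window is wrong as written. It excludes nothing, for medications and procedures alike, and so defeats the section's own purpose. The logic needs no assumption. The practical effect depends on unknown prior use: under the assumed 10% against 2%, the ratio of 5.0 falls to between about 3.0 and 1.1 for prior use of 2% to 40%, with prior and later use independent.

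Second, no planned output describes estradiol valerate after randomisation. For a participant still taking it at Day 63, that is about 71% or more of her exposure, given the protocol's limits before transfer.

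It would be tempting to go further and say that unreported estradiol changes bias the treatment comparison. They do not. Participants are analysed as assigned, and changes that follow from assignment are part of the effect of being assigned. What is missing is descriptive information on whether an observed difference in pregnancy or bleeding came with a difference in background treatment. The size of any such difference cannot be judged from the documents.

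**What to change.** - **SAP 12, both sentences:** replace *or* with *and*. Define concomitant as use that overlaps the SAP's existing treatment period (first dose after randomisation to last dose, as in 15.1), including use still ongoing. Keeping that period avoids a second time origin.
- **Prior medication:** show separately any treatment stopped before the first dose after randomisation.
- **Estradiol valerate:** add one descriptive by-arm table for the period after randomisation, giving duration, dose, dose changes and stops. First confirm that the eCRF captures dosing beyond Visit 3. If it does not, name estradiol changes among the data collected at Visits 4 to 6, in line with Protocol 6.5.

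The wording change costs nothing. The rest costs a prior-medication display, one estradiol table and possibly slightly more data entry. No endpoint analysis changes, and no dosing rule is implied.

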## 13 Study intervention Compliance and Exposure

All dosing calculations and summaries will be based on “Administration of Crinone” and “Administration of Duphaston” eCRFs pages.

Crinone will be administered prior to randomization, but first dose date after randomization will be used as start date in the following calculation.

### Analysis Population to be used for summaries:

- Safety population

### Compliance

- Compliance (%) = 100 \* actual dose/planned dose for study intervention duration.
  - Crinone Planned Dose: 90mg/gel, q.d
  - Duphaston Planned Dose: 10mg/tablet, b.i.d

**14 Efficacy Analyses**

**14.1 Primary Endpoint: Ongoing Pregnancy**

#### 14.1.1 Primary Objective: Analysis of the primary endpoint Ongoing Pregnancy

Analysis (Analysis Population)	Derivation	Statistical Analysis Methods	Missing data handling
Primary endpoint: Ongoing pregnancy assessment at 10-12 weeks of pregnancy [8-10 weeks after ET]			
Primary (ITT)	Ongoing pregnancy rate (%): =100 * number of subjects with ongoing pregnancy/number of subjects with ET cycle.	

Point estimate and 95%CI for each study intervention groups (Clopper-Pearson)

Point estimate and 90%CI for difference between two study intervention groups (stratified Miettinen & Nurminen (MN) method (see Miettinen & Nurminen, 1985))

It will be computed with the SAS® 9.4 FREQ procedure, using the riskdiff (COMMON) option in the Table statement and specified alpha=0.1. The results could be found in the ODS CommonPdiff table (method=' Summary Score')

	Missing=Failure
Supportive (PP)	

Time window: from the start date of first ET to the end of study.

Numerator: The subjects with ongoing pregnancy will be determined to be those with positive ongoing pregnancy result in the "Ongoing Pregnancy Assessment" eCRF page

Denominator: The subjects with ET cycle will be determined as those with ET date in "Embryo Transfer" eCRF page.

		

#### 14.1.2 Subgroup Analyses of the primary endpoint Ongoing Pregnancy

Since the number of embryos transferred is medically known to have an impact on the chance of achieving an ongoing pregnancy rate, the rate of subjects with only 1 embryo transferred within each arm will be examined by fisher exact test. If the data suggest a possible imbalance between the two arms ( $p<0.05$ ), then subgroup analyses of the primary endpoint in subjects with only 1 embryo transferred and in subjects with 2 embryos transferred may be performed with the method same in 14.1.1.

#### 14.2 Secondary endpoint

Analysis (Analysis Population)	Derivation	Statistical Analysis Methods	Missing data handling
Secondary Endpoint: <math>\beta</math>-hCG positive			
Secondary (ITT)	$\beta$ -hCG positive rate (%): =100 * number of subjects with positive $\beta$ -hCG /number of subjects with ET cycle.	Same as method in the section 14.1.1	Next observation carried backward (NOCB). Missing assessment outcomes prior to positive pregnancy assessment outcome will be imputed to be positive. Note: imputation is only valid for those subjects with following positive assessment outcomes and carried backward. Otherwise, missing=failure.
Supportive (PP)	
 
Time window: from the start date of first ET to the end of study.
 
Numerator: The subjects with positive <math>\beta</math>-hCG will be determined to be those with positive <math>\beta</math>-hCG result in the "<math>\beta</math>-hCG Level" eCRF page at <math>\beta</math>-hCG positive assessment visit.
 
Denominator: The subjects with ET cycle will be determined as those with ET date in "Embryo Transfer" eCRF page.
 
		
Secondary Endpoint: Implantation			
Secondary (ITT)	Implantation rate (%): =100 * number of gestational sacs observed / number of embryos transferred.	Same as method in the section 14.1.1	Same as above
Supportive (PP)	
 
Time window: from the start date of first ET to the end of study.
 
Numerator: The number of gestational sacs will be obtained in the "Clinical Pregnancy Assessment" eCRF page.
 
Denominator: The number of embryos transferred will be obtained in the "Embryo Transfer" eCRF page.
 
		
Secondary Endpoint: Clinical pregnancy			
Secondary (ITT)	$\beta$ -hCG positive rate (%): =100 * number of subjects with clinical pregnancy/number of subjects with ET cycle.	Same as method in the section 14.1.1	Same as above
Supportive (PP)	
 
Time window: from the start date of first ET to the end of study.
 
		

	
 
Numerator: The subjects with clinical pregnancy will be determined to be those with positive clinical pregnancy result in the "Clinical Pregnancy Assessment" eCRF page
 
Denominator: The subjects with ET cycle will be determined as those with ET date in "Embryo Transfer" eCRF page.
 
		
Secondary Endpoint: Early abortion			
Secondary (ITT)	Early abortion rate (%): =100 * number of subjects with Early abortion/number of subjects with clinical pregnancy.	Same as method in the section 14.1.1	Missing=not occurred
Supportive (PP)	
 
Time window: from the start date of first ET to the end of study.
 
Numerator: The subjects with Early abortion will be determined to be those with early miscarriage date in "early miscarriage" eCRF page.
 
Denominator: The subjects with clinical pregnancy will be determined to be those with positive clinical pregnancy result in the "Clinical Pregnancy Assessment" eCRF page.
 
		

